### 7.7.3 Vital signs

Visit values and changes from baseline for vital sign measurements (pulse, blood pressure, SpO2, temperature, respiratory rate) will be summarized by treatment group at each visit using descriptive statistics. Visit values will be calculated as the mean of all available measurements per parameter.

## 7.8 Interim analysis

For safety issues or evidence of poor efficacy, the DSMB could recommend stopping enrollment at any time; no formal interim analysis for this segment of the trial will be performed.

Group-level unblinded summaries of the immunogenicity and safety data will be produced once Week 6 visit immunology data and Week 8 visit safety data are complete for all subjects who have not discontinued, while maintaining subject-level blinding. Long-term follow-up data will continue to be collected for all subjects who have not discontinued with remaining visits through the final visit. These summaries will allow the Sponsor to have results for the purposes of dose selection for the Phase 3 portion. No subject-level immunogenicity data will be produced, and subject-level immunogenicity data will not be available in the clinical trial database until all other clinical trial data are finalized at the end of the trial. No safety summary will be provided if the total number of subjects who experience the event of interest is greater than 0 and the count of the number of subjects with the event in a given treatment group relative to the total produces a percentage less than 3%, for a given summary. The group-level unblinded production of the summaries will not include anyone directly involved with the trial or any additional unblinded personnel; only the external Contract Research Organization (CRO), ICON, which will already be providing unblinded summaries for the Data Safety

Monitoring Board, will be utilized. Thus, the trial will remain blinded to the Sponsor with respect to subject treatment assignment.

Based upon the wide availability of EUA and licensed vaccines in the US and completion of the data collection towards the Phase 3 dose selection, the Sponsor recognizes that subjects may want to know whether they received INO-4800 or placebo in order to make fully informed choices about receiving a non-study prophylactic COVID-19 vaccine (either authorized under emergency use or when licensed). Therefore, once all subjects have reached the Week 30 Visit timepoint, all subjects will be unblinded (as specified in study protocol USA v2.0).

### 8 Changes to Planned Analysis from Study Protocol

Not applicable.

## Statistical Analysis Plan (SAP) – Phase 3 Segment

### Revision History

Version	Date	Revisions
0.1	29-September-2021	Initial draft
0.2	29-September-2021	Revised draft after internal review.
0.3	17-November-2021	Revised draft addressing comments from sponsor.
0.4	22-June-22	The study has been terminated, analysis will be restricted to primary efficacy and safety.
0.5	04-July-2022	Revised following sponsor comments.
1.0	27-Jul-22	Update schedule of assessments from protocol version 6 and removed lab analyses Final version

### 1. Introduction

The purpose of this Statistical Analysis Plan (SAP) is to provide detailed descriptions of the statistical methods, data derivations, and data displays for study protocol COVID19-311 version 6.0 "Phase 2/3 Randomized, Blinded, Placebo-Controlled Trial to Evaluate the Safety, Immunogenicity, and Efficacy of INO-4800, a Prophylactic Vaccine against COVID-19 Disease, Administered Intradermally Followed by Electroporation in Healthy Seronegative Adults at High Risk of SARS-CoV-2 Exposure" dated 30 April 2021 for the analysis of the Phase 3 segment of the trial. The table of contents and templates for the Tables, Listings, and Figures (TLFs) will be produced in a separate document.

Any deviations from this SAP will be described and justified in the Clinical Study Report (CSR).

The preparation of this SAP has been based on International Council for Harmonization (ICH) E9 and Good Clinical Practice (GCP) guidelines.

#### 1.1 Study Objectives

The overall purpose of this clinical trial is to evaluate the safety, immunogenicity, and efficacy of INO-4800 to prevent COVID-19 in subjects at high risk of exposure to SARS-CoV-2.

##### 1.1.1 Primary objective

The primary objective of this clinical trial is to evaluate the efficacy of INO-4800 in the prevention of COVID-19 disease in subjects who are SARS-CoV-2 negative at baseline.

##### 1.1.2 Secondary objectives

The secondary objectives of this clinical trial are:

1. To evaluate the safety and tolerability of INO-4800.
2. To evaluate efficacy of INO-4800 in the prevention of COVID-19 disease according to degrees of disease severity in subjects who are SARS-CoV-2 seronegative at baseline.
3. To evaluate the cellular and humoral immune response to INO-4800.
4. To evaluate the efficacy of INO-4800 in the prevention of COVID-19 disease in subjects who are SARS-CoV-2 seropositive at baseline.

##### 1.1.3 Exploratory objectives

The exploratory objectives of this clinical trial are:

1. To evaluate the efficacy of INO-4800 in the prevention of COVID-19 disease from SARS-CoV-2 variants in subjects who are SARS-CoV-2 seronegative at baseline.
2. To evaluate the efficacy of INO-4800 in the prevention of SARS-CoV-2 asymptomatic infection in subjects who are SARS-CoV-2 seronegative at baseline.

## Statistical Analysis Plan (SAP) – Phase 3 Segment

3. To evaluate the immunological profile by assessing both antibody response and T cell immune response.
4. To evaluate antibody persistence.

### 1.2 Study Design

#### 1.2.1 Design Configuration

This SAP pertains to the Phase 3 segment of an operationally seamless Phase 2/3, randomized, placebo-controlled, multi-center trial to evaluate the efficacy, safety, and immunogenicity of INO-4800, administered by ID injection followed immediately by EP using the CELLECTRA® 2000 device, in a 2-dose regimen (Days 0 and 28) in adults who are at high risk of SARS-CoV-2 exposure. The subjects and data from Phase 3 are independent from that of Phase 2. Approximately 6714 seronegative and 402 seropositive subjects 18 years of age and older will be randomized at a 2:1 ratio to receive either active investigational product (INO-4800, 2.0 mg) or placebo (SSC-0001). Approximately half of seronegative subjects and approximately half of seropositive subjects will be 18-50 years of age, and the other half will be  $\geq 51$  years of age as is operationally feasible. Also, approximately 711 subjects will be  $\geq 65$  years of age, if operationally feasible.

The Phase 3 segment of the trial is case-driven. Among seronegative subjects, a total of 149 observed cases will be required for 90% power to declare the vaccine efficacious ( $>30\%$ ), assuming a true efficacy of 60%. A sample size of 6714 seronegative subjects is expected to be required to achieve the 149 cases assuming an underlying attack rate of 3.7%. The actual sample size may differ if the observed attack rate is different than projected. There are two formal interim analyses of efficacy; one when 50% of the cases accrue and one when 75% of the cases accrue. If the prespecified criteria for efficacy are met at either interim analysis, then enrollment will continue until 4500 subjects have been enrolled, and blinded follow-up will continue until at least those 4500 subjects have a minimum of 6 months of safety follow-up. At that point, the trial would be unblinded and placebo-recipients will be offered the active product.

The study's primary efficacy endpoint is the incidence of virologically-confirmed COVID-19 disease in subjects who are SARS-CoV-2 seronegative at baseline starting 14 days after completion of the 2-dose regimen until 12 months post-dose 2. All subjects will be followed for 56 weeks from the Day 0 dosing (i.e., Week 56 will be the planned End of Study [EOS] visit for this segment of the trial).

The total study duration is 393 days from screening to study discharge/EOS.

The Data Safety Monitoring Board (DSMB) will convene regularly to review all available unblinded efficacy and safety data. Additionally, an independent, blinded Endpoint Adjudication Committee (EAC) will review and confirm COVID-19 cases.

#### 1.2.2 Randomization and Blinding

## Statistical Analysis Plan (SAP) – Phase 3 Segment

This study is double blinded. Approximately 6714 seronegative and 402 seropositive subjects 18 years of age and older will be randomized at a 2:1 ratio to receive either active investigational product (INO-4800, 2.0 mg) or placebo (SSC-0001). See [Table 1](#). Approximately half of seronegative subjects and approximately half of seropositive subjects will be 18-50 years of age, and the other half will be  $\geq 51$  years of age as is operationally feasible. Also, approximately 711 subjects will be  $\geq 65$  years of age, if operationally feasible.

Randomization in this trial will be conducted by YPrime. Subjects will be randomized in a stratified manner according to (a) age category (18-50 years vs.  $\geq 51$  years) on Day 0, and (b) presence of or absence on Day 0 of any of the following underlying medical conditions that increase risk of severe COVID-19 disease, per CDC criteria, as listed below:

- Cancer
- Chronic kidney disease
- Chronic lung diseases, including Chronic obstructive pulmonary disease (COPD), asthma (moderate-to-severe), interstitial lung disease, cystic fibrosis, pulmonary hypertension
- Neurologic conditions including stroke or cerebrovascular disease, that do not impact cognition
- Diabetes (type 1 or type 2)
- Hypertension
- Heart conditions, such as heart failure, coronary artery disease, or cardiomyopathies
- HIV infection (CD4 count  $>200$  cells/mm $^3$  or undetectable viral load)
- Liver disease
- Obesity (BMI  $\geq 30$  kg/m $^2$ )
- Sickle cell disease or thalassemia, or
- Smoking (current or former smoker).

**Table 1: Sample Size for Randomization**

Treatment Arm	Sero status	Expected Number of Subjects	Approx. Expected Number of Subjects by Age Group		Dosing Days	Number of Injections + EP per Dosing Visit	INO-4800 (mg) per injection	INO-4800 (mg) per Dosing Visit	Total Dose of INO-4800 (mg)
			18-50	51+ a					
INO-4800	Seroneg	4476	2238	2238	0, 28	2	1.0	2.0	4.0
	Seropos	268	134	134					
Placebo	Seroneg	2238	1119	1119	0, 28	2	0	0	0
	Seropos	134	67	67					
Total	Seroneg	6714	3357	3357					
	Seropos	402	201	201					
Total		7116							

aat least 711 subjects will be  $\geq 65$  years of age

This Phase 3 segment of the clinical trial is case-driven. Among seronegative subjects, a total of 149 observed cases will be required for 90% power to declare the vaccine efficacious (>30%), assuming a true

## Statistical Analysis Plan (SAP) – Phase 3 Segment

efficacy of 60%. A sample size of 6714 seronegative subjects is expected to be required to achieve the 149 cases assuming an underlying attack rate of 3.7%. The actual sample size may differ if the observed attack rate is different than projected. There are two formal interim analyses of efficacy; one when 50% of the cases accrue and one when 75% of the cases accrue. If the prespecified criteria for efficacy are met at either interim analysis, then enrollment will continue until 4500 subjects have been enrolled, and blinded follow-up will continue until at least those 4500 subjects have a minimum of 6 months of safety follow-up. At that point, the trial would be unblinded and placebo recipients will be offered the active product.

Study staff at each site (coordinators and PI) along with the participants, and sponsor representatives will be blinded throughout the course of the trial. At ICON, unblinded personnel will consist of a biostatistician and statistical programmer. The DSMB members will also be unblinded. Emergency unblinding procedures may be taken if the knowledge of the product administered is essential for the medical management of the participant by the principal investigator. Individual, emergency participant unblinding will be conducted through the IRT system. Notification to sponsor and medical monitor and associated documentation will be made for each unblinding.

Formal unblinding of the trial will be done after database lock and after identification and approval of the per-protocol analysis set.

### 1.2.3 Study Duration

The maximum duration for study participation from screening to end of follow-up period is 393 days.

### 1.2.4 Study Treatments and Assessments

The investigational product (IP) INO-4800 is formulated in sodium chloride and sodium citrate buffer, refrigerated. Placebo (sterile saline sodium citrate buffer [SSC-0001]), refrigerated.

Dosing regimens in Phase 3 Segment:

- Active Investigational Product: Two 1.0 mg ID injections of INO-4800 (~0.1mL dose volume) followed immediately by EP administered in separate limbs on Day 0 and Day 28 ( $\pm 3$  days).
- Placebo: Two ID injections of SSC-0001 (~0.1mL) followed immediately by EP administered in separate limbs on Day 0 and Day 28 ( $\pm 3$  days).

Once eligibility has been confirmed, the subject will be randomized to receive a treatment assignment (INO-4800 or placebo). Visit dates and windows must be calculated from Day 0, unless otherwise noted. All subjects will be followed until the Day 393 Visit. All subjects will be followed in accordance with assessments outlined in the Protocol 6.1.2.

The Data and Safety Monitoring Board (DSMB) will advise regarding any safety concerns and will make recommendations regarding continued enrollment, safety pause, and trial suspension. If the safety data are considered unfavorable during any safety review, the DSMB may recommend a trial pause or trial termination. The Sponsor will perform an investigation and consult with the DSMB and other experts, if

## Statistical Analysis Plan (SAP) – Phase 3 Segment

needed, to determine whether to resume dosing of the remainder of the subjects. For further details, see the DSMB Charter.

The detailed descriptions of procedures and assessments to be conducted during this study are summarized in the Phase 3 Schedule of Events in [Appendix A](#).

### 1.2.5 Sample Size and Power

The Phase 3 segment of this trial is case-driven. A total of 149 observed cases among baseline SARS-CoV-2 seronegative subjects will be required to provide 90% power to declare the vaccine efficacious (>30%), assuming a true efficacy of 60%, with a one-sided type 1 error of 0.022. A sample size of 6714 baseline SARS-CoV-2 seronegative subjects will be required to achieve 149 cases assuming an underlying attack rate of 3.7%. The actual sample size may differ if the observed attack rate is different than projected.

## 2. Types of Planned Analyses

### 2.1 Data Safety Monitoring Board Analyses

The DSMB will meet approximately monthly until all subjects are enrolled in the trial, then bimonthly once all subjects are enrolled for the duration of the trial. The DSMB may also meet ad hoc as needed outside of the scheduled meetings and shall be disbanded upon completion of the trial.

The following data/documents will be generated for DSMB review:

- Baseline characteristics, demographics, participant disposition.
- Adverse events (AEs), adverse event of special interest (AESI), medically attended adverse events (MAAEs), and serious adverse events (SAEs).
  - Tabulated for each trial group by system organ class (SOC) and preferred term (PT), severity, seriousness, duration, treatment given, and the relationship to the trial drug and device.
  - Clinical test results and laboratory values (including raw values, changes from baseline, and clinical abnormalities).
- Listing of administration (injection) site reactions, including grading, duration, and treatment provided.
- Listing of deaths.
- COVID-19 disease.
- Any other supporting data requested by the DSMB.

### 2.2 Interim Analyses

Two formal interim analyses of efficacy are planned for review by the independent DSMB, as described in the clinical protocol and in the DSMB Charter: one at 50% (75 cases) and one at 75% (112 cases) of the total required cases for the primary endpoint (149 cases). However, the trial has been terminated prior to

observing 75 cases, and therefore, these analyses will not be conducted. For safety issues, the DSMB could recommend stopping enrollment at any time; no formal interim analysis will be performed for this purpose.

Therefore, the two-sided type I error of 0.05 will not be adjusted for interim analyses.

### 3. General Considerations for Data Analysis

#### 3.1 Analysis Populations

##### 3.1.1 Intention-To-Treat population (ITT)

The ITT population includes all subjects who are randomized, regardless of protocol violations or missing data. Subjects in this sample will be grouped to treatment arms as randomized. Analysis of the ITT population will be considered supportive for the corresponding Per-Protocol population for the analysis of efficacy.

##### 3.1.2 Modified Intention-To-Treat population (mITT)

The mITT population includes all subjects who receive at least one dose of study treatment. Subjects in this population will be grouped to treatment arms as randomized. Analysis of the mITT population will be considered supportive for the corresponding Per-Protocol population for the analysis of efficacy.

##### 3.1.3 Safety population (Safety)

The safety analysis population includes all subjects who receive at least one dose of study treatment. Subjects will be analyzed according to the treatments received.

##### 3.1.4 Per-Protocol population (PP)

The PP population includes all subjects who receive all doses of study treatments and have no protocol violations. Subjects in the PP population will be grouped to treatment arms as randomized. Subjects excluded from the PP population will be identified and documented prior to unblinding of the trial database. Analyses of the PP population among those who are baseline SARS-CoV-2 seronegative will be primary for the analysis of efficacy.

#### 3.2 Strata and Covariates

SARS-CoV-2 serostatus at baseline will be used as a stratification factor for several analyses. No covariates will be included in the analyses.

#### 3.3 Multiplicity

Not applicable.

#### 3.4 Derived Variables

Derived variables for demographic and baseline characteristics, various duration derivations, and other derivations are listed in [Table 2](#).

## Statistical Analysis Plan (SAP) – Phase 3 Segment

**Table 2: Derived Variables**

Variables	Formula
Demographic and Baseline Characteristics	
Body Mass Index	Weight (kg) / [height (m)] ^2
Derivation of Durations	
Study day at any visit	Date of interest – date of first dose of trial vaccine. One day is added if the difference is $\geq 0$ .
Duration of any events	End Date of Event – Start date of event + 1
Baseline Derivations	
Baseline	The baseline value is defined as the last observation prior to or on the date of the first dose of study drug; missing data will not be imputed.
Change from baseline	Post baseline value – Baseline; missing data will not be imputed.
Other Derivations	
Incidence	The number of subjects with a specific event divided by the total follow up time (in days) among the subjects in the treatment or control group and at risk of an initial occurrence of the event.
p	The true proportion of subjects with disease who receive INO-4800 relative to the total number of subjects with disease.
k	
The total amount of follow-up time (in days) in the placebo group divided by the total amount of follow-up time (in days) in the INO-4800 group
 
For calculating k, an individual subject's follow-up time is either:
 
 
the date of first disease diagnosis – date of the start of surveillance period + 1 (for subjects who are cases), or
 
the date of last follow-up – date of the start of surveillance period + 1 (for subjects who are non-cases).
 
 
The primary hypothesis of relative efficacy greater than 30% will be tested with <math>H_0: p \geq .70/(.70+k)</math> vs. <math>H_1: p < .70/(.70+k)</math>.

Vaccine Efficacy	1 – Risk in the vaccinated group / Risk in the unvaccinated group* 100, where risk is defined as the number of subjects with disease divided by the number of subjects in risk. Also equal to $(1-(1+k)p)/(1-p)$ , where k and p are defined above.
Confidence interval for efficacy	$[(1-(1+k)UBp)/(1-UBp), (1-(1+k)LBp)/(1-LBp)]$ , where UB and LB are the Clopper-Pearson upper and lower limits for the proportion, p; and p and k are defined above.
Geometric mean titer (GMT)	GMT is calculated as anti-log 10 (mean [log 10 Ti]) where Ti is the assay result for subject i.
Geometric mean fold rise (GMFR)	GMFR is calculated as anti-log 10 (mean [log 10 (Yi/ Bi)]) where Yi is the post dose assay result for subject i; and Bi is the baseline assay result for subject i.

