### 3.6 General Statistical Conventions

All statistical procedures will be completed using SAS version 9.4 or higher.

Unless otherwise stated, all statistical testing will be two-sided and will be performed using a significance (alpha) of 0.05. Two-sided 95% confidence intervals (CI) will be provided when relevant.

Continuous variables will be summarized using descriptive statistics, including number of subjects (n), mean, median, standard deviation (SD), minimum, and maximum. Means and medians will be rounded to one more decimal place than what is reported in the data. Standard deviations will be rounded to two more decimal places than what is reported in the data.

For categorical variables, summaries will include counts of subjects and percentages. Percentages will be rounded to one decimal place.

For summary purposes, baseline will be defined as the last available pre-dose value. All summaries will be presented by treatment group and SARS-CoV-2 serostatus at baseline, unless otherwise specified.

For any subject who receives an approved COVID19 vaccine after being dosed with INO-4800/placebo, the follow-up time will be divided to account for pre- and post- receipt of approved vaccine. For the main analyses and summaries of efficacy, data from the pre- receipt of an approved vaccine period will be used.

Subject data, including those derived, will be presented in individual subject data listings. Unless otherwise stated, unscheduled visit results will be included in date/time chronological order, within patient listings only. All listings will be sorted by treatment, subject ID, date/time, and visit. The treatment group, as well as the patient's sex and age, will be stated on each listing. Unless otherwise stated, data listings will be based on all subjects randomized (ITT population).

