## Statistical Analysis Plan (SAP) – Phase 3 Segment

amount of follow-up time in the INO-4800 group. For calculating k, an individual subject's follow-up time is either:

- the date of first disease diagnosis – date of the start of surveillance period +1 (for subjects who are cases), or
- the date of last follow-up – date of the start of surveillance period +1 (for subjects who are non-cases).

However, the trial has been terminated, and therefore, this hypothesis test will not be conducted. A confidence interval (detailed in the following section) will be used for analysis.

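### Phase 3 SAP Table 2 equates a risk-based vaccine efficacy with a person-time formula that is a different quantity, and its rule for k is not reconciled with the split of follow-up in section 3.6

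*SAP*

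**What the plan says.** All references are to the Phase 3 SAP.

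- **Section 3.4, Table 2, Vaccine Efficacy row.** VE is one minus the risk in the vaccinated over the risk in the unvaccinated, "where risk is defined as the number of subjects with disease divided by the number of subjects in risk. Also equal to" the expression (1-(1+k)p)/(1-p), with k and p taken from the same table.
- **Table 2, p and k rows.** p is "The true proportion of subjects with disease who receive INO-4800 relative to the total number of subjects with disease". k is "The total amount of follow-up time (in days) in the placebo group divided by the total amount of follow-up time" in the INO-4800 group.
- **Table 2, Incidence row.** Incidence is cases over total follow-up days, which is a rate.
- **Table 2, confidence-interval row, and section 5.1.3.** Both put the Clopper-Pearson limits for p through the person-time formula. Section 5.1.3 contains no risk ratio.
- **End of follow-up for k.** Table 2 ends the time of subjects without disease at "the date of last follow-up – date of the start of surveillance period + 1 (for subjects who are non-cases"). Section 5.1.2 repeats the rule.
- **Section 3.6.** For a subject who receives an approved COVID-19 vaccine after study dosing, follow-up time is split at that receipt. Then: "For the main analyses and summaries of efficacy, data from the pre- receipt of an approved vaccine period will be used".

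**The concern.** The row that defines the primary efficacy measure names two quantities and declares them equal. One divides cases by subjects, the other by days at risk. Someone programming from that row could report a risk-based point estimate beside a rate-based interval, and the output need not look wrong.

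The measure carries the whole efficacy result. The trial was terminated before 75 cases, the hypothesis test was dropped (sections 5.1.2 and 5.1.5), and no secondary or exploratory efficacy endpoint will be analysed (sections 5.2 and 5.3). What remains is the estimate, its interval and the mITT and ITT supportive versions.

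The secondary issue concerns k. Its operational rule is written out twice, and neither place mentions the split at receipt of an approved vaccine. The rule also has only two branches, case and non-case. It does not say where time ends for a subject who falls ill after an approved vaccine and whose illness therefore lies outside the main-analysis period.

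**Working it through.** **1. The plan's own figures.** Allocation is 4476 to 2238, so k = 0.5 if mean follow-up is equal. With a 3.7% placebo attack rate and a true VE of 60%, expected cases are 4476 x 0.037 x 0.4 + 2238 x 0.037 = 66.2 + 82.8 = 149.05, matching the stated 149. With p0 = 0.70/(0.70 + 0.5) = 0.5833 and p1 = 0.40/(0.40 + 0.5) = 0.4444, the exact binomial test on 149 cases rejects at 74 or fewer INO-4800 cases. Its one-sided error is 0.0201 (0.022 allowed) and its power is 0.9135 (90% stated). The sample size reproduces and is not affected by this point.

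**2. Algebra.** Write x_v and x_c for cases, T_v and T_c for follow-up time, and N_v and N_c for subjects (v = INO-4800, c = placebo). Then p = x_v/(x_v + x_c), p/(1-p) = x_v/x_c and k = T_c/T_v.

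(1-(1+k)p)/(1-p) = 1 - k p/(1-p) = 1 - (x_v/T_v)/(x_c/T_c)

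This is one minus a rate ratio. The risk version is 1 - (x_v/N_v)/(x_c/N_c). They coincide only if T_c/T_v = N_c/N_v, that is, if mean follow-up per subject is equal. The null boundary in section 5.1.2 is also on the rate scale: setting k p/(1-p) = 0.70 gives p = 0.70/(0.70 + k).

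**3. Size of the gap.** The SAP gives no follow-up by arm, so the imbalances below are assumptions. For a fixed rate ratio of 0.4, risk VE = 1 - 0.4 x (INO-4800 mean follow-up / placebo mean follow-up):

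| Follow-up ratio, INO-4800 / placebo | Rate VE | Risk VE |
|---|---|---|
| 0.9 | 60% | 64% |
| 1.0 | 60% | 60% |
| 1.1 | 60% | 56% |

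Cases themselves stop contributing time, so even a common observation period leaves a trace. With constant hazards, a 3.7% placebo risk and a rate VE of 60.0%, risk VE is 59.5%.

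The same comparison with cases fixed at an assumed 66 and 83 gives a risk VE of 1 - 0.5 x 66/83 = 60.2%, whatever the follow-up. If placebo mean follow-up is 0.90 times INO-4800, k = 0.45 and the rate VE is 1 - 0.45 x 66/83 = 64.2%, with a Clopper-Pearson interval of 50.0% to 74.5%. A risk estimate of 60.2% would sit inside that interval without attracting notice.

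**4. The rule for k.** If section 3.6 were not applied to k, the value used would be 0.5 under equal total follow-up. The value matching the counted cases would be 0.5 x (placebo share of time before outside vaccination) / (INO-4800 share). With a true VE of 60%, the reported VE is 1 - 0.5 x 0.4/k_true:

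| Assumed share, placebo / INO-4800 | k_true | Reported VE |
|---|---|---|
| equal | 0.500 | 60% |
| 75% / 85% | 0.441 | 54.7% |
| 60% / 80% | 0.375 | 46.7% |

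These shares are illustrations, since the SAP gives no uptake figures. If placebo recipients were instead vaccinated less or later, the error would run the other way.

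**The case against.** **On the definition.** Section 5.1.3 fixes the primary analysis with one formula, derives it from a Poisson model conditioned on total cases, and uses the same transformation for the interval. A programmer who follows it will not mix the two quantities. The trial is randomised and blinded, and staggered entry or early termination does not by itself unbalance mean follow-up between arms. Precision is also low: with an assumed 33 of 74 cases on INO-4800 and k = 0.5, VE is 59.8% with an interval of about 35% to 75%, so a shift of a few points lies well inside it. All of this stands and limits the weight. It does not make the stated equality true.

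**On k.** A reader might infer that the plan cuts off cases at an approved vaccine while letting time at risk run on. The documents do not support that. The sentence in section 3.6 just before the one quoted says that follow-up time itself is divided at receipt, and time is what k is built from. On a plain reading both time and cases are limited to the period before receipt. What survives is that the specific rule, written twice, neither carries nor cites the general one. The 54.7% and 46.7% figures are therefore not a forecast of bias in this trial.

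**Conclusion.** The equality in Table 2 is false as written. The person-time formula is one minus an incidence-rate ratio and matches the risk definition only with equal mean follow-up per subject. The difference is about half a point with a common observation period at the planned attack rate, and about four points at VE 60% under an assumed 10% imbalance in follow-up. Nothing in the SAP shows that such an imbalance exists. Because section 5.1.3 and the interval row already use the rate form, this is a definition to correct, not evidence that the result will be wrong. It is still worth correcting, since it defines the only efficacy measure to be reported.

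The rule for k is an unreconciled definition. It changes the estimate only if section 3.6 is overlooked when k is computed and, in addition, uptake of approved vaccines or its timing differs by arm.

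**What to change.** 1. In Table 2, delete the risk-based definition and the statement of equality. Define VE = 100 x [1 - k p/(1-p)], and use it for both the point estimate and the interval, as section 5.1.3 already does.
2. In Table 2 and section 5.1.2, state that for the main efficacy analysis a subject's follow-up for k ends at the earliest of first case, receipt of an approved COVID-19 vaccine as in section 3.6, end of the surveillance period, or last follow-up. State that the same end date decides which cases count.

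The cost is SAP wording and one derived end-date variable, settled before unblinding. Sample size and data collection are unchanged.
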